1. RESEARCH OVERVIEW / ABSTRACT (LIMIT 500 CHARACTERS)

There is an urgent need to engage co-users of tobacco and cannabis (CB) in evidence-based treatments that lead to better cessation outcomes. A significant number of cigarette smokers who call state quitlines (QL) for help quitting tobacco report using cannabis and are interested in reducing or quitting cannabis. Adding a brief intervention to address cannabis simultaneously

with standard tobacco cessation counseling may lead to improved tobacco cessation outcomes and reduce cannabis use.

2. STUDY PURPOSE & OBJECTIVES

Our specific aims are to:

- Develop an integrated tobacco/cannabis (CB) intervention utilizing key components of the Marijuana Check-up (MJCU, a brief behavioral intervention for increasing motivation to reduce or quit using cannabis). We will adapt the MJCU intervention for integration into tobacco cessation counseling; develop the intervention manual and training materials, and pilot test the new treatment with 10 QL callers who use CB. Our team includes an author of the MJCU, [name] at the University of Washington who will assist with development, training, and implementation of the integrated intervention.
- 2) Conduct a small, randomized pilot trial of the integrated intervention compared with the standard QL (treatment as usual; TAU) to evaluate feasibility, acceptability, and preliminary effectiveness with 100 co-users recruited from 4 participating state QLs. We will assess implementation factors, coach fidelity, treatment engagement, and outcomes at 3 months (satisfaction, tobacco cessation (biochemically verified), and CB use).

We hypothesize that the intervention will: (1) be feasible to deliver (measured by coach treatment fidelity scores); (2) be acceptable to co-users (measured by enrollments and call completion numbers); (3) increase tobacco cessation rates compared with TAU; (4) increase co-users' motivation to change CB use; and (5) will produce greater reduction or cessation of CB.

Significance: This study comes at a critical time to answer key questions posed by state and local health departments who are considering the best methods for reaching CB users and increasing treatment utilization. Nationally, QLs have expressed concerns about the potential growth of co-users calling quitlines and the need to address the impact this has on treatment outcomes.

Public Health Relevance: Smoking cigarettes remains the number one preventable cause of death and disease in the US. Smokers who call QLs and use cannabis may struggle to quit due to the interactive effects of nicotine and CB. The proposed brief behavioral intervention addressing co-use may increase QL callers' chances of achieving and maintaining tobacco abstinence as well as increase their motivation to reduce CB use. As non-medicinal CB use becomes more common and legal in more states, a low touch intervention for co-users of CB and tobacco could improve health outcomes for many. Findings will inform development of scalable public health intervention strategies for co-users easily implemented across QLs.

3. JUSTIFICATION & BACKGROUND

Background and Significance

Tobacco use remains the number one preventable cause of illness and death in the US. Targeted therapies are needed for priority populations. Tobacco use causes more than 480,000 deaths each year and for each of those deaths there are 30 people living with serious smokingrelated illnesses. [1] Tobacco use also costs the US economy an estimated \$300 billion from health care costs and lost productivity. While smoking rates in recent years have dramatically decreased in the general population, they have remained almost unchanged in people with mental health conditions, including substance use disorders [2]. Cannabis (CB), is the most common illicit substance used today, but is increasingly becoming legal [4]. As of 2018, thirty-three states and the District of Columbia (DC) have legalized CB in some form and 10 states and DC have legalized non-medical CB use (Alaska, California, Colorado, Maine, Massachusetts, Michigan, Nevada, Oregon, Vermont, and Washington). According to a 2017 survey, 14.6% of US adults used MJ in the past year, 8.7% in the past 30 days [5]. Use appears higher in states with legalized non-medical CB (20%) than in states with only legalized medical CB (14%) or no legal use (12%) and inversely correlated with age, with younger adults using at higher rates than older adults. [5]

Co-users of tobacco and CB have more difficulty quitting either substance and are at higher risk for tobacco-related illnesses. Recent longitudinal research shows that MJ users are more likely to start smoking cigarettes, continue to smoke over time (as opposed to quitting), and to relapse once quit. [18] Indeed, daily use of CB is associated with a 3.6 fold increase in nicotine dependence. [19, 20] Furthermore, nicotine is far more addictive than CB, works on the same neural pathways as CB [21], and cross-sensitization to each substance is likely to occur, with tobacco directly enhancing the subjective effect of CB, [12, 22, 23] leaving co-users more likely to develop a cannabis use disorder. [24]

Optum is the service provider for publicly funded tobacco cessation QL in 20 states and for more than 750 commercial clients with their Quit For Life coaching program. QLs are the primary method of accessing tobacco cessation services in the US and offer free services to any US resident. QL services include phone coaching, nicotine replacement medications (e.g., the nicotine patch), and digital services such as text messaging, a web intervention and a mobile app.

Co-users of tobacco and CB are at risk for continued tobacco dependence and associated serious health consequences of using both substances. CB use hinders smoking cessation efforts and tobacco use is a predictor of poor outcomes of CB dependence treatment. Our understanding of what is effective to reach and help co-users quit tobacco and CB is limited. Within this gap of knowledge is whether co-users who call tobacco cessation quitlines for help with cessation would benefit from an integrated phone-based program with CB elements based on the Marijuana Check-up (MJCU), the most widely used intervention for CB. Accordingly, we propose to develop and test a brief phone-based intervention for co-users of tobacco and CB for delivery in a quitline setting.

4. STUDY DESIGN

1. Design

D.4. Phase 2: Preliminary effectiveness pilot randomized controlled trial.

Overview. QL registration agents, coaches and/or research staff at Optum will screen for CB use and other study eligibility criteria and enroll participants into their respective state quitline. Once confirmed eligible, consented participants will complete the baseline assessment and be randomized into standard QL treatment as usual (TAU) or the experimental treatment, QL-CBCU. Approximately 3 months after randomization, we will email participants a link to the follow-up survey (with instructions). For those who fail to complete the online survey after two emails, we will send participant contact information via a secure transmission protocol to an external survey group who will attempt to complete the survey by phone, making 11 attempts at

different times of day and on different days. Those who do not complete the interview within 14 days will be emailed a reminder to take the full online survey or an optional brief online survey. Our research team will monitor completed surveys to identify those who reported they had not smoked tobacco in the past 7 days and request a biochemical validation test from participants as explained below (See section D.8.2. Biochemical Validation).

D.4.1. Setting. Participants will primarily be recruited from incoming callers from four state tobacco QLs with fully legalized CB use (Alaska, Washington DC, Oregon, Washington). See letters of support. These four QLs offer four or five proactive coaching calls, mailed support materials, access to text messaging, and web-based programs, plus at least two weeks of free NRT. If recruitment rates are slow, an alternative strategy of recruiting from social media (e.g., Reddit) will be implemented. All eligibility criteria will remain the same.

There will be two behavioral interventions tested in this trial; the standard quitline (treatment as usual: TAU) and the standard QL plus an adapted version of the CBCU (QL-CBCU). Both are phone based, brief, and utilize similar behavior change techniques: motivational interviewing (MI) and cognitive behavioral therapy (CBT). Both interventions include 4-5 proactive counseling calls, mailed materials, and at least 2 weeks of NRT. The new QL-CBCU intervention is being designed to be integrated into the quitline setting and delivered by quitline coaches with minimal training and infrastructure adaptation.

1. Duration

Participation will take about 3 months. The entire duration of the study is approximately 3 years.

Table 2. Self-Report Measures	Screen	Baseline	3-month follow-up
Demographics	Х	Х	
Chronic Conditions and Health Problems	Х		
Mental Health (PhQ2, GAD, PSS)		Х	
Alcohol Use		Х	
TO & E-Cigarette Use	Х	Х	Х
Motivation for Quitting TO		Х	
Cessation Medication use			Х
CB Use		Х	
Marijuana Problem List (MPL) & CUDIT		Х	Х
Motivation for Quitting/Reducing CB Use	Х		Х
CB Quit Goals and Impact on TO Use	Х		Х
Outcomes			
Program satisfaction and acceptability (usefulness,			v
would recommend the program to others)			^
7- and 30-day point prevalence tobacco			×
abstinence			~
Cannabis use (days/ week; occasions/day; hours		Х	X
of intoxication)		~~~~~~~~~~~~~~~~~~~~~~~~~~~~~~~~~~~~~~~	

2. Metrics and Variables

3. Data

The sources of research materials obtained from individual human subjects in the study are limited to records and data, which will be available to the study team. Records include number and duration of counseling calls automatically collected by Optum. Data will be in the form of self-report questionnaires collected on the phone or via the internet and stored in a secure computer assisted telephone interview (CATI) system or via a secure link to a survey collection database. The 3-month follow-up survey may be completed via an online secure survey sent by Optum or telephone survey conducted by an external survey team. For participants who do not respond to the online or phone surveys, the research team will email participants a reminder to complete the full online survey or an brief online survey. There will also be biochemical verification of tobacco use at 3 months post randomization.

4. Materials

Emailed and mailed letters An emailed outcomes survey Saliva test kit

5. Devices – N/A

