Recruitment for the study will have two methods. The primary method begins by screening for CB use during enrollment with the quitline and assessing eligibility and interest in the study. Optum's computer system will provide initial pre-screening so that only callers from participating quitlines who are 21+ years old are screened for the study. Registration agents will ask additional screening questions including CB use for at least 9 days in the last 30, interest in quitting smoking within 30 days, ready access to phone and email, screen negative for serious mental illness (schizophrenia), and whether they have an interest in study participation. The secondary recruitment method will be recruiting from ads on location specific social media sites (e.g., the r/Washington site on Reddit). Interested participants will email the study research assistant who will screen participants over the phone and enroll them into their respective state quitline if eligible. All participants will be contacted by phone by research-trained coaches who will describe the study in more detail, obtain informed consent, and deliver the baseline assessment and the post-randomization script.

Additionally, after the baseline assessment participants will be randomly assigned to receive the standard QL intervention (TAU) or the integrated intervention (QL-CBCU). All participants will receive the follow-up assessment (outcomes) survey at 3 months.

7. Enrollment / Consent Plan and Materials

Research-trained coaches will describe the study in more detail, read the information/consent document verbatims- and obtain verbal informed consent.

8. Compensation/Remuneration/Reimbursement

Incentives

Participants will receive \$30 after completing call 1 (for the baseline assessment and call 1 participation), \$20 for completing the second coaching call, \$50 for completing the follow-up survey or \$25 for a partially completed follow-up survey or a brief survey in lieu of the full follow-up survey, and \$20 for completing the biochemical validation test. Participants will also have an option to complete the online survey within 48 hours of the email informing them to complete the survey for an additional \$25 bonus. These incentives will be provided to all participants and both study groups (TAU and QL-CBCU). A randomly selected group of participants in the experimental group will be invited to complete a post intervention interview with the PI or the Co-I and receive \$25 upon completion.

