Participants self-reporting tobacco abstinence 7 or more days at follow-up will be sent a test to confirm their abstinence by biochemical verification (saliva). Before sending the biochemical verification kit, study staff may contact the participant via email with an alert that a biochemical verification kit with instructions will be mailed to them and can be tracked with the provided USPS tracking number. A cover letter will be included in the kit explaining how to complete the test, instructions for returning the results via a photo to the study team's email box, and 14 day requested timeline for submitting the results. Instructions in the kit will inform participants to not eat or drink 10 minutes prior to taking the saliva test. Participants will be directed to refrain from including any PII in this email. If the results are not received within 7 days of delivery, a follow up email reminder may be sent. If the test outcome is returned by the participant, study staff will send the participant a \$20 gift card for their participation (regardless of test outcome).

2. Subject Participation

Participant experience in the study:

Day 1.

SCREENING- Participant will answer questions if interested in study participation.

- INFORMED CONSENT If interested and eligible, participant will hear the consent form read to them by the Quit Coach. The participant may ask questions before giving their consent. The Quit Coach will note the participant has provided their verbal informed consent. The participant will be mailed a copy of the consent.
- **BASELINE SURVEY** Participant will spend approximately 20 minutes answering baseline assessment questions.
- FIRST COACHING CALL Participant will engage in coaching call about quitting smoking with some discussion of how cannabis use will affect their quit attempt. Afterwards they will be sent a gift card for \$30.
- **EMAIL PFR** Participant will be sent a feedback report based on their answers to the assessment questionnaire.
- COACHING CALL 2 Participant will be contacted by phone second coaching call which will focus on interaction of tobacco and cannabis and the feedback report. Participant will be paid \$20 following this call.

FOLLOW UP COACHING CALLS. Participants will be contacted for 2-3 more calls to discuss how their smoking quit is going and follow up on cannabis use and goals. 2/3 months following enrollment:

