For the proposed pilot study we plan to use summary statistics (means and proportions) with confidence intervals (CIs), and standard errors (SE), and graphical displays (histograms, pie charts, Box plots, etc.), as appropriate, to describe participant self-reported demographic characteristics, use of tobacco and cannabis, and other tobacco and cannabis variables measured at baseline and/or at each coaching call and at 3-months. We will use Fisher's exact tests, t-tests, and Wilcoxon rank sum tests to compare intervention and control groups. Comparisons including mean number of calls completed, mean satisfaction ratings, mean change in cigarettes per day (CPD), and mean change in days of cannabis use will be completed. We also will compare groups on changes over time on other cannabis measures, including hazardous cannabis use. We will address the effect of missing values on estimated smoking cessation rates using sensitivity analyses for outcome measures: 1) we will analyze responders only, and 2) we will impute missing tobacco use as 'smoking'.

We will have sufficient power with 100 participants (50 per group) and a 70% response to the follow-up interview to detect significant effects of the integrated intervention (vs. standard treatment controls) on feasibility and acceptability of the QL-CBCU intervention as measured by calls completed and treatment satisfaction at 3 months. This sample size is also sufficient for estimating QL-CBCU's potential impact (compared with the standard quitline) measured at 3 months on tobacco abstinence and CB outcomes (motivation to reduce days using CB, confidence in avoiding CB over-use, decreased problems associated with CB use, and decreased frequency of use). The sample sizes for this feasibility study are sufficient for the conduct and reporting of stage I pilot studies and were not selected for purposes of detecting statistically significant group differences at the alpha .05 level on outcomes. Our sample size is sufficient for documenting what power is available. For ordinal measurements that can statistically be treated in a similar manner to "continuous" measures (such as the number of QL calls completed and days used CB), we have 80% power to detect an effect size of 0.68. For proportions, we are powered to detect a difference in proportions of 0.22 to 0.34 (depending on the proportions in the two groups).

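### Calls completed is compared as a pooled mean with no denominator, although some quitlines offer four calls and others five; comparing arms within the number offered is a small, nearly free improvement

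*Combined protocol and SAP*

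**What the plan says.** - **Calls offered.** Section 4, D.4.1 Setting: "These four QLs offer four or five proactive coaching calls". The same section says of the two arms: "Both interventions include 4-5 proactive counseling calls, mailed materials, and at least 2 weeks of NRT". Section 6, Subject Participation, agrees: after call 2, "Participants will be contacted for 2-3 more calls", which makes four or five in all. The protocol does not say which quitline offers which number.
- **Role of the measure.** Hypothesis 2 in Section 2 measures acceptability by enrolment and call completion. Section 6, Data Analysis, names calls completed as a measure of feasibility and acceptability.
- **Analysis.** Section 6, Data Analysis, plans "Comparisons including mean number of calls completed, mean satisfaction ratings". The methods named are Fisher's exact tests, "t-tests, and Wilcoxon rank sum tests to compare intervention and control groups". No denominator is given for calls, and no analysis uses state or quitline.
- **Randomisation.** Sections 4, 5 and 6 say that participants are randomised after the baseline assessment. No method, stratum or block size is described.
- **Timing.** Quitline is known before allocation. Callers enter through their state's quitline, and social-media recruits who are eligible are enrolled in theirs (Section 5, Recruitment Plan and Materials).

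**The concern.** Quitline is a baseline factor that fixes the ceiling of the count. When 4-call and 5-call quitlines are pooled, two things follow.

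First, the mean is hard to read as acceptability. A mean of 3.2 is 3.2/4 = 80% of what was offered in one type of quitline and 3.2/5 = 64% in the other. The pooled figure moves with the state mix, which the plan does not fix and which may shift if social-media recruitment starts or enrolment grows from 100 towards 230. Section 8 (Publication Plan) foresees using the findings to seek funding for a fully powered trial, so a mean and SD that depend on the mix could be carried forward.

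Second, the difference between the two types of quitline stays in the error term of the arm comparison, although a stratified test would remove it at almost no cost.

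**Working it through.** **1. The plan's own figure.** Section 6 states 80% power for an effect size of 0.68, with calls completed as an example. Inputs: 50 per arm, 70% response, so 50 x 0.70 = 35 per arm; alpha 0.05, taken as two-sided because sidedness is not stated. The normal approximation gives (1.960 + 0.842) x sqrt(2/35) = 0.670. The noncentral t gives 0.679, which reproduces 0.68.

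**2. Share of variance due to the number of calls offered.** Let w be the proportion of participants in 5-call quitlines, m4 and m5 the mean counts, and v4 and v5 the within-type variances.

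Share = w(1-w)(m5-m4)^2 / [w v5 + (1-w) v4 + w(1-w)(m5-m4)^2]

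Detectable effect after stratifying = 0.68 x sqrt(1 - share), in overall SD units.

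The protocol gives neither w nor completion rates. I assume w = 0.5 and two completion models:
- Sequential drop-out: everyone completes call 1, and a fraction c continues to each next call. Then m4 = 1 + c + c^2 + c^3 and m5 - m4 = c^4.
- Independent completion: each call is completed with probability p. Then m = kp and v = kp(1-p) for k calls offered.

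Worked case, p = 0.8: m4 = 3.2, m5 = 4.0, v4 = 0.64, v5 = 0.80. Within = 0.72, between = 0.25 x 0.8^2 = 0.16, share = 0.16/0.88 = 18.2%.

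| Model | m4 | m5 | Overall SD | Share | 0.68 becomes |
|---|---|---|---|---|---|
| Drop-out, c = 0.5 | 1.88 | 1.94 | 1.13 | 0.1% | 0.680 |
| Drop-out, c = 0.8 | 2.95 | 3.36 | 1.44 | 2.0% | 0.673 |
| Drop-out, c = 0.9 | 3.44 | 4.10 | 1.27 | 6.7% | 0.657 |
| Independent, p = 0.5 | 2.00 | 2.50 | 1.09 | 5.3% | 0.662 |
| Independent, p = 0.8 | 3.20 | 4.00 | 0.94 | 18.2% | 0.615 |

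The share becomes large only near full attendance: 15% at c = 0.95 and 33% at p = 0.9. With w = 0.25 or 0.75 the share is generally smaller.

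**3. Dependence of the pooled mean on mix.** Under drop-out with c = 0.8, the mean is 0.75 x 2.95 + 0.25 x 3.36 = 3.05 if a quarter are in 5-call quitlines, and 0.25 x 2.95 + 0.75 x 3.36 = 3.26 if three quarters are. Behaviour is identical in both.

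**4. Chance imbalance, if randomisation were simple.** The 95% range of the difference between arms in the 5-call proportion is 1.96 x sqrt(2 x 0.25/50) = +/-0.20 at 50 per arm, and +/-0.13 at 115 per arm. With w = 0.10 it is 1.96 x sqrt(2 x 0.09/50) = +/-0.12. At w = 0.5 and 50 per arm, 0.196 x 0.41 = 0.08 calls (c = 0.8) and 0.196 x 0.80 = 0.16 calls (p = 0.8).

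For comparison, call counts come from automatic records (Section 4, Data) and do not need the follow-up survey. All 50 per arm can therefore be used, and the detectable effect is 0.566 SD: 0.566 x 1.44 = 0.82 calls and 0.566 x 0.94 = 0.53 calls in the same two cases. The imbalance at its 95% limit is thus about a tenth to three tenths of the detectable difference.

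**5. Would the share of calls offered be a better single measure?** Not in general. Under drop-out with c = 0.8, the expected shares are 2.95/4 = 74% and 3.36/5 = 67%. Someone who stops after call 3 scores 75% in one type of quitline and 60% in the other. The share removes the difference between quitline types only if completion is proportional to the number offered.

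**The case against.** The strongest reply is that nothing here is wrong. A call count has a common unit; both arms are offered the same four or five calls by the same quitlines; an unstratified comparison is valid, and under simple randomisation its standard error already reflects chance imbalance in quitline. Section 6 says the pilot was not sized for significant differences, and acceptability also rests on enrolment and satisfaction. Using all 50 per arm for calls (0.68 to 0.57) helps more than stratifying does in most scenarios. All of this stands. It limits the point to efficiency and readability, but it does not remove the dependence of the pooled mean on mix.

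A reader might infer more than the documents support:
- *That the arm contrast is biased, or that the counts share no scale.* Neither follows. Only the ceiling differs, and it differs alike in both arms.
- *That a 0.8-call gap rivals the detectable effect.* That gap (p = 0.8) is between quitline types, not between arms. The effect on the arm contrast is the far smaller figure in step 4 of the working.
- *That NRT supply differs by quitline.* The text gives only a minimum, "plus at least two weeks of free NRT", and NRT does not set the scale of a call count.
- *That abstinence is distorted.* The protocol gives no figure for differences in abstinence between quitlines.
- *That randomisation is unstratified.* The method is not described, so one can say only that no stratification is stated.

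**Conclusion.** The point holds as a minor improvement. The ceiling of the count differs by quitline, the planned summary ignores this, and the pooled mean cannot be read as acceptability without knowing the mix. The arm comparison is unbiased on average. The avoidable variance is about 0.1-7% under sequential drop-out with 50-90% continuation, and about 5-18% under independent completion at 50-80%, so a detectable effect of 0.68 would fall to between 0.68 and 0.615.

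These figures assume an even split between 4-call and 5-call quitlines, the two completion models, and that the number of calls offered is fixed by quitline. The protocol supplies neither the split nor the completion rates.

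**What to change.** - **Section 4, D.4.1:** list the number of calls each quitline offers.
- **Section 6, Data Analysis:** compare calls completed between arms within the 4-call and 5-call strata, with a van Elteren test or a linear model with a term for calls offered (or quitline). Define the stratum by the offer of the quitline at enrolment.
- **Reporting:** give the distribution and mean of the count by arm and number of calls offered, with the share of calls offered beside it. The share should not replace the count, because under drop-out it creates a quitline difference of its own.
- **Randomisation, if not yet started:** stratify by 4- versus 5-call offer, counting social-media recruits in the quitline they enrol in. Keep block sizes concealed and varying, because the coaches who obtain consent also deliver the post-randomisation script and could otherwise anticipate the next assignment.

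The cost is about one degree of freedom, a stratified list and a few sentences. No new data are needed. If randomisation is already under way, the analysis and reporting changes can still be made.
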